COMIRB Protocol

COLORADO MULTIPLE INSTITUTIONAL REVIEW BOARD
[name] [contact] [contact]

Protocol #: 19-1366

Project Title: My Baby My Move+

Principal Investigator: [name]

Version Date: 5.6.21

I. Hypotheses and Specific Aims:

Statement of Purpose: The proposed study will implement and test the feasibility of a theoretically-based (e.g., social cognitive theory), peer-led wellness intervention, “My Baby My Move+” (MBMM+) to reduce excessive gestational weight gain (EGWG) by targeting physical activity, mood, and sleep.

The aims of the proposed research are to:

- Aim 1. Determine feasibility (i.e., acceptability and demand) of the MBMM+ program.
- Aim 2. Examine the impact of the MBMM+ program on EGWG at 12 weeks post-baseline to determine estimates of effect size for a future, larger randomized trial.

II. Background and Significance:

Up to 50% of pregnant women in the U.S. gain weight in excess of the Institute of Medicine (IOM) guidelines (i.e., excessive gestational weight gain (EGWG)). EGWG leads to poor maternal (e.g., pre-eclampsia, gestational diabetes, postpartum weight retention) and child (e.g., preterm birth, large for gestational age weight at birth) outcomes. It also sets the stage for long-term overweight/obesity for both mother and child. There are few efficacious intervention strategies for reducing EGWG and among those, physical activity is one promising strategy. Prenatal physical activity is associated with a variety of health benefits (e.g., reducing risks for gestational diabetes, pre-eclampsia, depression, and body image dysphoria). There is also a need to increase prenatal physical activity as approximately 80% of pregnant women are not meeting recommended levels. One reason for low prenatal activity is that pregnant women are concerned with and lack knowledge/skills about how to safely and effectively participate in physical activity. Increasing knowledge and skills about physical activity may improve prenatal physical activity participation, lower safety concerns, and in turn, reduce EGWG.

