participation in the program (to what extent they were satisfied with the program and parts of the program they enjoyed and parts they think could be stronger, etc). The interviews will be approximately 45 minutes long and you will be compensated \$30. Up to 15 women will be invited to participate in an interview. Due to COVID-19, the trial will be run two times; a remote pilot of the trial will be run in the Fall of 2020 (n=30), followed by a larger in-person trial (pending COVID-19) in the Spring of 2021 (n=70)

Interviews with participants will be conducted after the pilot trial (Fall 2020) in addition to after the full trial (Spring 2020).

B. Description of Population to be Enrolled:

We anticipate eligibility screening for pregnant women (6 through 12 weeks) to take approximately 5-10 minutes to complete. The time window for gestational age recruitment was selected based on our formative work [25] [26] that suggests that in order to impact EGWG early intervention is critical. The first 4 weeks of the intervention will consist of educational materials as women may not want to participate in physical activity until near the end of first trimester when their risk for miscarriage drops and the mother tends to feel better physically. The experiential component (i.e., walking and yoga) will start in week 5. In order to extend our recruitment window, we will create rolling recruitment opportunities with women entering into the program from weeks 1 through weeks 6 (weeks 1-4 electronic materials; weeks 5-6 zoom sessions begin). All women will receive the electronic materials for weeks 1-4 before starting the zoom group sessions in week 5. For those women who start the zoom sessions in week 6, they will receive an additional session (material from original week 5) at the end to ensure all women receive 16 sessions (8 weeks of zoom sessions). Women will be recruited from the University of Colorado Clinics, clinics in Denver Metro and surrounding areas as well as social media (e.g. facebook and instagram). We will work with providers to help with recruitment of women in need of intervention for EGWG.

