Sample Size. In terms of intervention effects on EGWG, results have been variable across studies, with average intervention effects being small to moderate. In terms of physical activity, our preliminary work with the original MBMM showed an effect roughly equivalent to Cohen's $d = 0.69$. This effect falls into the moderate range, similar to higher-impact interventions on EGWG [27]. Based on these two effect ranges, we estimated effect size to detect effects of $d > .63$, a medium effect, for the proposed MBMM+ intervention. Using this effect size, $\alpha = .05$, and $1-\beta = .80$, a sample size of 40 per arm (80 total) would be adequate to detect medium effects in EGWG, exercise, and other outcomes. We propose enrolling 50 per arm to account for up to 20% attrition and to allow for power to detect potentially smaller effects for EGWG. This level of power is expected to also be adequate for detecting changes in mediators, which have previously been observed to be more powerfully affected by the MBMM intervention than physical activity.

Due to COVID-19, the trial will be run two times; a remote pilot of the trial will be run in the Fall of 2020 (n=30), followed by a larger in-person trial (pending COVID-19) in the Spring of 2021 (n=70)

C. Study Design and Research Methods

Intervention Group:

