The MBMM+ intervention is designed to promote the engagement in physical activity and takes into account barriers among pregnant women cited in our formative work such as lack of knowledge and skills, body changes and discomfort, feeling limited, and lack of social support [24]. Uniquely, the MBMM+ program also targets sleep hygiene and mood to further support regular physical activity engagement. Over the years of working with pregnant women, we have observed that once women notice how their regular physical activity helps their mood and sleep patterns they are often more likely to continue engaging in regular physical activity. During the first four weeks of the MBMM+ program, participants will receive electronic informational handouts covering topics on weight management (content will be based in part on Co-I [name]' Healthy Mom Zone intervention such as informing on benefits and guidelines of healthy GWG, tips on healthy eating, energy balance, and sleep quality) [26] as well as the benefits and safety concerns related to prenatal physical activity. Starting week 5 of the 12-week intervention, participants will attend two virtual, group sessions per week with each session lasting approximately 30 minutes and will be held remotely via zoom. Sessions will be held on weekday evenings and weekend mornings as these times were preferred by pregnant women. Given that pregnant women often express a lack of knowledge about safe physical activities during pregnancy, preventing them from engaging in physical activity, each session will include both didactic and experiential components to increase knowledge and skill building. Sessions will begin with a didactic component covering overcoming barriers to physical activity, goal setting, self-monitoring, problem solving, topics related to mood (stress management, family/work balance, wellness wheel), sleep hygiene (setting routines, avoiding stimulants, environmental supports), and additional physical activity topics (e.g., managing physical activity in postpartum, overcoming relapses). Participants will be given educational materials in print and electronic form based on their preferences. Participants will then be encouraged to complete the experiential component (i.e., physical activity) on their own for 30 minutes in duration and involve primarily walking, at a moderate intensity, based on national recommendations [28] coupled with yoga. Yoga classes will be led remotely four times throughout the program. For these sessions, the online class will last 60 minutes; 15 minutes of didactic followed by 45 minutes of yoga. Our formative work suggests that mothers prefer walking and find it more enjoyable in the form of groups. We have chosen to also include yoga to provide options for ways to be active that also positively impact sleep and mood [16] [29] and pregnant women report desiring prenatal yoga [30]. All didactic sessions will be facilitated by the peer leaders (see below). The yoga sessions will be taught by an experienced prenatal yoga instructor residing in Denver, CO.

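### The one sample of 100 combines a 30-woman remote run with a 70-woman run of unclear delivery mode, and the analysis plan neither adjusts for run nor reports by run

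*Combined protocol and SAP*

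**What the plan says.** **Sample size (IV.B).** One effect size is set for one program: "we estimated effect size to detect effects of $d > .63$, a medium effect, for the proposed MBMM+ intervention". From it follows that "a sample size of 40 per arm (80 total) would be adequate to detect medium effects in EGWG, exercise, and other outcomes", and then "We propose enrolling 50 per arm to account for up to 20% attrition". The same subsection says that, because of COVID-19, "a remote pilot of the trial will be run in the Fall of 2020 (n=30), followed by a larger in-person trial (pending COVID-19"), n=70. Section IV.A repeats this sentence. IV.D (Recruitment and Informed Consent) confirms that up to 100 is the sum of 30 and 70 over two trials, but gives no delivery mode for the 70.

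**Delivery.** IV.C describes the intervention from week 5 as remote: "participants will attend two virtual, group sessions per week with each session lasting approximately 30 minutes and will be held remotely via zoom". The control sessions in IV.C are also on Zoom, and the population description in IV.B has all women receive electronic materials and then join Zoom groups. No in-person version of either arm is specified.

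**Between the runs.** IV.A states: "Interviews with participants will be conducted after the pilot trial (Fall 2020) in addition to after the full trial". The interviews are optional, for up to 15 women, and cover satisfaction and what could be improved.

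**Aims and analysis.** Aim 1 is to "Determine feasibility (i.e., acceptability and demand) of the MBMM+ program". Aim 2 seeks an effect size on excessive gestational weight gain for a later, larger trial. IV.F names five covariates (age, ethnicity, parity, risk status and socio-economic status). It does not mention run, delivery mode or how the runs are to be combined, and it does not say how feasibility will be summarised. IV.D allocates from a pre-generated table and mentions neither blocking nor stratification by run.

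**Dates.** The remote pilot is in Fall 2020 in IV.A, IV.B and IV.D, but in Fall 2021 in IV.C. The full trial is in Spring 2021 in IV.A, IV.B and IV.D, but also in Spring 2020 in the IV.A sentence on interviews. The version date is 5.6.21.

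**The concern.** Both aims produce inputs for a future trial: an effect size and a judgement on feasibility. If the second run is delivered in person, the two runs differ in ways that the protocol itself treats as relevant. In the Zoom program women walk on their own after the session, yet IV.C reports that mothers enjoy walking more in groups. Attending from home also asks less than travelling to a session, which bears on acceptability and demand.

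A combined estimate would then average two modes. With no run term and no by-run tables, a reader of the results could not tell whether the average describes either one. The same holds for attendance, retention and acceptability under Aim 1. At stake is what the results can be used for. The arithmetic of the sample size is not in question.

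**Working it through.** **Inputs.** From IV.B: alpha 0.05, power 0.80, d = 0.63, 40 per arm analysed, 50 per arm enrolled, 20% attrition, runs of 30 and 70. Assumed: a two-sided test, equal arms within each run and 20% attrition in each run.

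**1. The plan's own figure.** n per arm = 2(z₀.₉₇₅ + z₀.₈₀)²/d² = 2(1.960 + 0.842)²/0.63² = 39.55, rounded up to 40. Enrolment is 40/0.80 = 50 per arm, 100 in total. Both stated figures reproduce. A one-sided test would need only 32 per arm, so the calculation was two-sided.

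**2. Women analysed in each run.** Remote run: 30 × 0.80/2 = 12 per arm. Second run: 70 × 0.80/2 = 28 per arm. Since 12 + 28 = 40, the stated size is reached only with both runs together.

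**3. What each part can show.** Power and detectable d come from the two-sample t-test (noncentral t). The approximate 95% half-width is 1.96 × √(2/n), in SD units.

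| Women analysed | n per arm | Power at d = 0.63 | Detectable d at 80% power | Half-width |
|---|---|---|---|---|
| Both runs | 40 | 79% | 0.63 | 0.44 |
| 70-woman run | 28 | 64% | 0.76 | 0.52 |
| 30-woman run | 12 | 31% | 1.20 | 0.80 |

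**4. What a combined estimate averages.** The weights follow the sample sizes: 12/40 = 0.30 and 28/40 = 0.70. Combined d = 0.30 × d(run 1) + 0.70 × d(run 2). The run-specific effects below are assumed for illustration; the documents give none.

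- 0.63 and 0.63: combined 0.63, power 79%.
- 0 and 0.63: combined 0.44, power 50%.
- 0.63 and 0.30: 0.189 + 0.210 = 0.40, power 42%.
- 0 and 0.90: combined 0.63, which is true of neither run.

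The last case shows that a combined result equal to the planning value is no evidence that the runs agree.

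**5. Could the data settle whether the runs differ?** SE of the difference between the two run-specific effects = √(2/12 + 2/28) = 0.488 SD. The half-width is 1.96 × 0.488 = 0.96 SD. Power at a true difference of 0.63 SD is Φ(0.63/0.488 − 1.96) = about 25%. The difference detectable with 80% power is 2.80 × 0.488 = 1.37 SD. A non-significant arm-by-run test therefore could not justify pooling.

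**6. Allocation within the small run.** If allocation were unrestricted (not stated), the chance of a 10/20 or more uneven split among 30 is 2 × P(Binomial(30, 0.5) ≤ 10) = 0.099. After 20% attrition a 10/20 split leaves 8 and 16. The information, 1/(1/n₁ + 1/n₂), is then 5.33 instead of 6. With 14 from an evenly split second run, the total is 19.33 instead of 20, a loss of about 3% once run is in the model.

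**The case against.** Several stronger readings are tempting, and the documents do not support them.

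- *The trial will average two different programs.* In-person delivery is conditional and appears in one sentence, given in both IV.A and IV.B. Every description of how sessions are delivered is remote. If the second run also used Zoom, most of the argument about mode falls away.
- *The plan says the runs will be pooled.* No sentence does, and IV.D speaks of two trials. Pooling is inferred from the single N, the single effect size and the single-program aims. The inference is strong, because 40 per arm cannot be reached otherwise.
- *The program will be revised after the pilot interviews.* Nothing says so. The protocol leaves open whether content stays fixed.
- *The 80% power holds only if both runs share one effect.* It depends mainly on the average effect. The case of 0 and 0.90 averages 0.63, and power stays close to the stated figure.
- *Remote delivery works less well.* No figure supports this, and the lower powers in step 4 rest on assumed effects.
- *Aim 2 should come from the second run alone.* That is a debatable trade: it widens the half-width from 0.44 to 0.52 SD and drops 30% of the women from an estimation aim.

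It is also fair to say that combining the runs does not bias the arm comparison if allocation is balanced within each run, and that imbalance in the 30 would cost little precision once run is adjusted for. What stands is that the mode and dates conflict, and that neither the analysis nor the reporting lets run be seen.

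**Conclusion.** The point holds as a gap in specification and reporting. The sample size is arithmetically correct, but it is met only by the two runs together, and IV.F would let a combined effect size and feasibility result average two delivery modes without showing it. If the modes differ, the average is weighted about 30:70; how far it would miss either mode cannot be derived from the documents. The second run alone has about 64% power at d = 0.63 and detects about 0.76, given equal arms, 20% attrition in each run and a two-sided test. If the second run used the same Zoom program, the concern shrinks to the conflicting text and to ordinary differences between a pilot and a main run.

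**What to change.** 1. In IV.A to IV.D, reconcile the delivery mode of the 70-woman run with the delivery descriptions, and reconcile the run dates (pilot Fall 2020 or Fall 2021; full trial Spring 2021 or Spring 2020). State whether the 30 count toward the 100.
2. In IV.D, use a separate blocked allocation list for each run not yet allocated. On the Fall 2020 date the pilot would already have been allocated before this version, so the change could then apply only to the later run. In IV.F, include run as a covariate in all models.
3. Keep the pooled, run-adjusted estimate for Aim 2. Beside it, report the effect with a 95% interval for each run and the arm-by-run difference, labelled descriptive because of its half-width of about 0.96 SD and power of about 25%.
4. Report Aim 1 attendance, retention and acceptability by run.
5. In IV.B, state that the 80% power at d = 0.63 applies to both runs combined, and give the figures for the 70-woman run alone (about 64%; detectable d about 0.76).

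The cost is protocol wording, an allocation list per run, one more model term and a few table columns; no extra women are needed. The drawbacks are wide run-specific intervals and a less favourable stated figure for the second run alone.

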mindfulness, wellness wheel, family/life balance) and sleep (good sleep hygiene, sleep/energy balance) given their inter-relatedness to EGWG and physical activity, 3) add a comprehensive objective assessment of physical activity, 4) add an appropriate comparison group that controls for time and attention (i.e. health education group); 5) add yoga as a programmatic activity component throughout program, and 6) increase participant/peer leader contact time by addition of more small group participant interactions with peer leaders. To do so, we will increase the length of intervention from eight to 12 wks as well as the dose from one session/wk to two sessions/wk.

IV. Research Methods

A. Outcome Measure(s): The Assessment Table (Table 1) displays all primary and secondary outcomes, associated measures, and the timeline of data collection. Data will be collected at four timepoints: T1) baseline, T2) 6-weeks post-baseline, and T3) 12- week post-baseline (i.e. end of intervention) and T4) at time of delivery.

Assessment tools (scale and Fitbit) will be delivered to participants after eligibility is confirmed and after they complete the online consent and baseline survey at a time and location of their choosing. A scale and Fitbit with a brief one-page protocol will be delivered to the participants by the Study Coordinator. Seven-days after delivery, the Study Coordinator will pick up the Fitbit (from all participants) and scale (from control participants). The participants will leave these materials at a specific location for the Study Coordinator. There will be no contact between them. During this time, the Study Coordinator will either drop off a hard copy of the curriculum (or send an electronic copy) as well as incentives for the intervention group participants (yoga mat and pedometer). The team has instituted strict protocols to minimize exposure related to COVID-19. This includes:

- No contact with participants; the Study Coordinator will leave the materials mentioned above at a specific location dictated by the participant (e.g. front porch).
- The Study Coordinator will wear a mask at all times when doing deliveries of assessment and programmatic materials.
- The Study Coordinator will complete a symptoms checklist and take their temperature prior to dropping off assessment and programmatic materials. This will be shared with the PI prior to delivery.

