
For the remote pilot trial in the Fall of 2021, each session will have one lead Peer Leader and one additional peer leader to help facilitate the sessions and support goal setting. Our MBMM formative work and expertise in community-based physical activity interventions suggests participants prefer peer group leaders because they foster a sense of community and social support within the group setting [23]. Peer leaders will be compensated for their time working with the MBMM+ program and will be peer mothers from the community who are recent mothers (< two years postpartum) who successfully engaged in regular

physical activity during a previous pregnancy. Peer leaders will be identified by our research team, recreation center directors, and health care provider partners. At the end of every didactic session, participants will check in with an assigned peer leader to discuss in small groups their weekly logs. The team will use the ‘breakout room’ feature in zoom to divide the larger group into their smaller groups for these discussions. Peer leaders will note the discussions that occurred amongst the participants in their group, describe barriers that were identified, problem-solving strategies that were suggested and used, and future goals/recommended action steps. This group work will help participants to learn ways to fit physical activity into their lifestyle and overcome barriers by receiving feedback from their peer leader and other group members. It will also ensure that the intervention is conducted and received in the way intended as the peer leaders and program manager/PI will review these small group progress notes each week and monitor intervention delivery.

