Peer leader training and fidelity: Weekly, the research team will have phone calls with the group peer leaders to debrief and address any issues that may arise. At least one member of the research team will participate in all sessions to ensure quality control of intervention delivery and data collection efforts by peer leaders. The PI will conduct a training session delivered remotely before the onset of the intervention with the peer group leaders to cover topics including how to engage in safe and effective physical activity during pregnancy, an overview of behavioral change theory and the behavioral skills that the intervention is targeting, ways to garner social support and leadership skills. The PI has been extensively trained by the Cooper Institute in Prenatal-Postnatal Physical Activity. The yoga instructor will have been extensively trained in prenatal yoga.

Control Group:

Women randomized to the control group will complete a similarly structured 12-week program; electronic materials related to various prenatal topics including preparation for birth, birthing options, and responsive parenting will be distributed twice a week for the first 4-weeks of the program. Starting week 5 of the 12-week intervention, participants will attend two virtual, group sessions per week with each session lasting approximately 45 minutes. Sessions will be held remotely via zoom. Sessions will be held on weekday evenings and weekend mornings as these times were preferred by pregnant women.

The Intervention-group Table of Contents and Control-group Table of Contents displays all key topics presented throughout the 12-week intervention and control groups. Please find study materials for intervention and control arms in the Appendix.

D. Description, Risks and Justification of Procedures and Data Collection Tools

Recruitment and Informed Consent. Participants for this study will be recruited from obstetric clinics located in the Aurora and Denver Metro and surrounding areas, as well as facebook and instagram. The investigators and study staff have completed NIH-approved training for human subject-based research, and are experienced at consenting subjects according to federal guidelines. Up to 100 pregnant participants will be recruited to

complete this study (two trials; remote pilot in the Fall of 2020 with 30 participants followed by larger trial in the Spring of 2021 with 70 participants).

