This is an important and fundamental study that needs to be conducted to meet the need for effective, sustainable community-based interventions to reduce EGWG. Because pregnancy is an opportune time to adopt healthy behaviors such as physical activity, there is a definite need for intervention at this time. The MBMM+ intervention has been designed based on feedback from pregnant women from recent formative and pilot work to develop an intervention that is attractive and unique to this population. The intervention includes a strong social support component as our formative work and extant literature clearly demonstrate lower levels of attrition in interventions providing social support. Moreover, the addition of the small group interaction after each session will provide further opportunity to build rapport and strengthen interpersonal support and a sense of group membership. Third, self-regulation techniques that support maintenance of physical activity and its interrelatedness of mood and sleep will be used. All of these supports can show successful community-based interventions to reduce EGWG.

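### Women are randomised individually but treated in groups, and the power and models assume independence; if the groups make outcomes alike, the Aim 2 standard error is too small and the 80% power too high

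*Combined protocol and SAP*

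**What the plan says.** IV.D (Recruitment and Informed Consent) randomises each woman individually from a computer-generated table. IV.C (Intervention Group) then delivers treatment in groups: from week 5 "participants will attend two virtual, group sessions per week with each session lasting approximately 30 minutes". The control arm has the same structure: "participants will attend two virtual, group sessions per week with each session lasting approximately 45 minutes".

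Intervention women have a further layer. After every didactic session "participants will check in with an assigned peer leader to discuss in small groups their weekly logs". For the remote pilot, "each session will have one lead Peer Leader and one additional peer leader to help facilitate the sessions". No small groups are described for controls.

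The plan expects the groups to have an effect. Section III lists as an enhancement to "increase participant/peer leader contact time by addition of more small group participant interactions with peer leaders". IV.C says that women learn by "receiving feedback from their peer leader and other group members". IV.G says that "the small group interaction after each session will provide further opportunity to build rapport and strengthen interpersonal support and a sense of group membership".

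IV.B (Sample Size) uses only an effect size of 0.63, alpha 0.05, power 80% and up to 20% attrition to reach 40 analysed and 50 enrolled per arm. IV.F names latent growth curve models adjusted for age, ethnicity, parity, risk status and SES. Neither section mentions session group, small group, peer leader or trial run. Aim 2 is to supply effect-size estimates for a larger randomised trial.

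**The concern.** Individual randomisation does not make outcomes independent once women are treated together. If a leader or a set of groupmates shifts the outcomes of everyone in the group, those women carry less separate information than the same number treated alone. A model that ignores this gives a standard error that is too small.

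Here the plan relies on group interaction as part of how the intervention works, yet its power and its models assume that groupmates' outcomes are unrelated. What is at stake is the precision attached to the Aim 2 effect. The next trial would be planned on an estimate that looks more certain than it is, and the 80% power would be too high. IV.B enrols 50 per arm, which gives some power margin, but better retention does not correct a standard error that is too small.

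**Working it through.** **Inputs from the plan.** d = 0.63, alpha 0.05 (two-sided is assumed, since a one-sided test gives 32 per arm and not 40), power 80%, 40 analysed and 50 enrolled per arm (IV.B); pilot of 30 women (IV.B); two peer leaders per pilot session (IV.C). Total variance is set to 1.

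**Reproducing the plan's figure.** n per arm = 2 × (1.960 + 0.842)² / 0.63² = 39.6, so 40, and 40 / 0.80 = 50. With the t distribution, SE = √(2/40) = 0.2236 and 0.63 / 0.2236 = 2.82; on 78 df this gives 79.5% power. Both calculations use independent women and no design effect.

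**Assumptions that the plan does not supply.** Neither ICC nor group size is given. There is one rough anchor for size: half of 30 is 15 intervention women in the pilot, and two leaders imply small groups of 7 to 8, or 12 / 2 = 6 after 20% attrition, if all attend one session. Nothing comparable is given for the run of 70.

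**Formulas.** For groups of size m the design effect is DE = 1 + (m − 1) × ICC. For unequal groups, replace m by Σm²/n. SE = √((DE + 1)/n) if only the intervention arm is grouped and √(2 × DE/n) if both arms are. Power uses the noncentral t with 2n − 2 df. Type I error is that of the unadjusted two-sample t-test, simulated under the null.

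Pairs are intervention arm only / both arms, with 40 analysed per arm:

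| Groups | ICC | DE | SE | Type I error | Power |
|---|---|---|---|---|---|
| independent | 0 | 1.00 | 0.224 | 5.0% | 79.5% |
| 8 of 5 | 0.01 | 1.04 | 0.226 / 0.228 | 5.2% / 5.5% | 78.7% / 77.9% |
| about 6 (five of 6, two of 5) | 0.05 | 1.24 | 0.237 / 0.249 | 6.4% / 7.9% | 75% / 71% |
| 5 of 8 | 0.02 | 1.14 | 0.231 / 0.239 | 5.8% / 6.6% | 76.7% / 74.1% |
| 5 of 8 | 0.05 | 1.35 | 0.242 / 0.260 | 7.1% / 9.2% | 72.8% / 66.8% |

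In the last row a nominal 95% interval covers about 93% / 91%.

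**If all 50 per arm are retained.** With groups of about 8 and ICC 0.05, power is 82% / 77% (87.7% if independent), but type I error is still 7.2% / 9.4%.

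**If the whole session is the cluster.** Suppose one group per arm in each run, 12 and 28 women after attrition. Then Σm²/n = (144 + 784)/40 = 23.2, and ICC 0.01 gives DE = 1 + 22.2 × 0.01 = 1.22 and type I error 6.3% / 7.7%.

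**If the likeness is only sorting.** Independent outcomes were sorted within arm into 5 groups of 8 on a trait correlated 0.22 with the outcome, inducing an ICC of about 0.05. The unadjusted test stays at 5.0%.

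The t-test simplifies the covariate-adjusted growth model. IV.A also classifies weight gain as above, within or below guidelines, so these figures are a guide to size and not predictions for the planned analysis.

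**The case against.** The strongest reply is that the group effect may be close to zero. The first four weeks are electronic handouts. Apart from four yoga classes, women do the activity by themselves, and group contact is two short online sessions a week. Leaders share one training, have weekly debriefs, and work with a research team member present at every session (IV.C, Peer leader training and fidelity). All of this may keep the ICC low, and nothing in the documents favours 0.05 over 0.01. This stands, and it is why the point is conditional.

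Three further objections also stand in part:

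- **Sorting.** "Sessions will be held on weekday evenings and weekend mornings as these times were preferred by pregnant women", and entry is rolling, so women who share a session may be similar to begin with. That alone would not inflate the planned test, and an observed ICC cannot separate it from a group effect.
- **Control arm.** The both-arms figures apply intervention small-group sizes to controls, who share sessions but have no described small groups. For a given group size they are an upper scenario.
- **Covariates.** If covariates explained 25% of the variance but left the group variance unchanged, power with groups of 8 and ICC 0.05 would be 82.5% / 75.6%, against 89.5% for independent women. They could restore some power but would not remove the gap.

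A reader might also infer that group membership will be lost unless action is taken now. The documents do not support that for the intervention arm: leaders are assigned, and their small-group notes are reviewed weekly, so membership is largely recoverable. Control session membership is not described.

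That this is a feasibility study does not dispose of the point, because IV.B makes a formal power claim and Aim 2 feeds a larger trial. No interval is named for Aim 2, so the issue concerns whatever standard error or interval accompanies the estimate.

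**Conclusion.** The concern holds in conditional form. The plan treats women as independent in both the sample size and the models while delivering treatment in groups that it expects to matter. If the groups themselves make outcomes alike, the standard error of the Aim 2 effect is too small and the 80% power too high.

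The omission is certain and its size is not. With 40 analysed per arm it runs from negligible (groups of 5, ICC 0.01) to a loss of about 7 to 13 power points with type I error of about 7% to 9% (groups of 8, ICC 0.05, intervention arm only to both arms). Larger clusters would raise it further.

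Two stronger readings are tempting and are not supported. One is that the effect estimate is biased: in this setting ignoring grouping affects its precision and not its expected value. The other is that the trial is underpowered and must enrol more. With groups of 8 and ICC 0.05 in both arms, 39.6 × 1.35 = 53.4, or 54 analysed per arm, would be needed, but that rests on an ICC and a control group size that the documents do not give.

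**What to change.** 1. **Data fields.** Record session group and trial run for every woman in both arms, and small group/peer leader in the intervention arm, as named analysis variables.
2. **IV.F.** Keep the planned growth model and add one supplementary interval for the Aim 2 effect that allows for grouping. With enough groups, use a partially nested model (group effect in the intervention arm) with a small-sample df correction. Otherwise widen the planned interval by the design effect at fixed ICCs, for example 0.01, 0.02 and 0.05. Set in advance what counts as enough, and state that an observed ICC is imprecise and cannot separate group effects from sorting.
3. **IV.B Sample Size.** State that the 80% assumes independent women, and give power over a short range of ICC and group size. Do not add participants on this account. If covariate-adjusted power is quoted, say whether covariates are assumed to reduce the group variance.

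The cost is wording and a few identifier fields. The downsides are a wider supplementary interval and a less favourable stated power:

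- With 5 groups of 8 and ICC 0.05, the simulated mean 95% half-width rises from 0.44 to 0.52 SD under the partially nested model. It is already 0.47 at ICC 0 because of the df correction.
- If the likeness is only sorting, that analysis is conservative (type I error 3.7%).
- With two groups per arm (12 and 28), estimating the group effect in both arms gives half-widths of 0.93 to 1.24 SD, which is unusable. The fixed-ICC route gives 1.991 × √(2 × DE/40) = 0.49, 0.53 and 0.65 SD at ICC 0.01, 0.02 and 0.05 (DE 1.22, 1.44 and 2.11), against 0.445 for independent women.
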